10.2.2 Interim analysis

We will conduct three interim-analyses; one when 10% of participants have been followed for 30-days, one when 30% of participants have been followed for 30-days and one when 50% of participants have been followed for 90-days. The Data Monitoring and Safety Committee (DMSC) will analyse only the fluid volumes and protocol violations in the two intervention groups in the two interim analyses to ensure that separation is occurring. At the third interim analysis they will assess fluid volumes, protocol violations, the 90-day mortality and the rates of SAEs and SARs in the ICU in the two intervention groups as described in the charter (Appendix 4). The DMSC will submit their recommendations to the Management Committee, which make the final decision regarding the continuing, pausing or stopping of the trial as described in the DMSC charter.

10.2.3 Early stopping criteria

The trial will not be stopped unless the cumulative Z-value for effect size supersedes the Lan DeMets group sequential monitoring boundary corresponding to a P-value for effect of less than 0.005

The CLASSIC trial protocol Page 33/82

(approximately). The trial will not be stopped for futility as an intervention effect less than a 15% relative risk reduction may be clinically relevant. However, the DMSC can recommend pausing or stopping the trial if continued conduct of the trial clearly compromises participant safety.

10.2.4 Accountability procedure for missing data/population for analysis

If less than 5% of data are missing for any primary or secondary outcome, a complete case analysis without imputation of missing values will be performed. If missing data are more than 5%, a statistician masked for the intervention will assess whether data are 'missing completely at random' (MCAR criterion) based on a rational assessment of the pattern of missing data [48]. Little's test will be used if doubt remains [49]. If it is concluded that data are not MCAR, multiple imputation using chained equations will be performed by creating 10 input datasets under the assumption that the data are 'missing at random' (MAR criterion) [50, 51]. We will use outcomes and the most important baseline characteristics in the multiple imputations as will be outlined in the detailed statistical analysis plan.

If multiple imputations are used, then the primary result of the trial will be based on these data. The unadjusted, non-imputed analysis will also be presented. If multiple imputation is used because of missing outcome data, we will use a best-worst worst-best case scenario as a sensitivity analysis to assess the potential impact of any pattern of missingness including that the data are 'missing not at random' (MNAR criterion). In the 'best-worst-case' scenario it is assumed that all participants lost to follow-up in the experimental group have had a beneficial outcome (e.g. have survived, had no SAE etc.); and all those with missing outcomes in the control group have had a harmful outcome (e.g. have not survived; have had a SAE etc.). Conversely, in the 'worst-best-case' scenario, it is assumed that all participants who were lost to follow up in the experimental group have had a harmful outcome; and that all those lost to follow-up in the control group have had a beneficial outcome. When continuous outcomes are used, a 'beneficial outcome' will be defined as the group mean plus two SD of the group mean or highest possible value whichever is smallest, and a 'harmful outcome' will be defined as the group mean minus two SD of the group mean or lowest possible value whichever is highest.

11 Quality control and quality assurance

The Sponsor and the coordinating investigator will be responsible for organizing the trial sites including education of local investigators, research nurses, and other trial site personnel before the initiation of the trial. This education will be continuously documented in the site master file. An annual investigator meeting will be planned.

After initiation, trial site investigators will be responsible for all trial-related procedures at their site, including education of staff in trial-related procedures, recruitment and follow-up of participants and entry of data. Clinical staff at the trial sites will be responsible for the treatment of trial participants.

The CLASSIC trial protocol Page 34/82

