10.2 Statistical methods

The analyses will be done in the intention-to-treat (ITT) population defined as all randomised participants for whom there is consent for the use of data. We will perform the primary analyses adjusted for the stratification variables [45] and challenge the primary result in analyses adjusted for important baseline risk factors (co-morbidities, higher SMS score, and focus of infection (other foci vs. urinary tract infection)[43, 46] and use of corticosteroids, which may reduce the time in ICU and thus the time exposed to the protocol [47]) and analyses of subgroups (Table 2) and the per-protocol population being the ITT population except those having one or more major protocol violations as defined below (Table 3). If there is more than 5% missing data for outcomes and/or covariates, we will impute the missing data using multiple imputations as described below (10.2.4).

All analyses will be 2-tailed and we will use Fisher's exact test for unadjusted comparisons of dichotomized outcomes (mortality at 90-days and 1-year, SAEs and SARs) and logistic regressions for adjusted analyses of these outcomes. The remaining secondary outcomes are continuous measures; we expect that these are highly skewed (non-normally distribution), because of inflation of specific values such as zero for days alive outside hospital for all patients who die while at the ICU. We will use statistical methods that can accommodate this type of data; the precise models will be specified in the detailed statistical plan.

Several of the secondary outcome measures are composite; we will also analyse each component of these outcomes as recommended [42]; the precise models will be specified in the detailed statistical plan.

Table 2. Heterogeneity of the intervention effects on the primary outcome will be analysed in the following subgroups based on baseline characteristics

Subgroup	Definition	Expected direction of	Statistical test
		the interaction	
Participants who are mechanically ventilated	Invasive mechanically ventilated (yes/no)	Larger effect of fluid restriction in mechanically ventilated participants	Test of interaction in the adjusted analysis described above; P- value 0.01

The CLASSIC trial protocol Page 32/82

Participants with	KDIGO (creatinine)	Larger effect of fluid	Test of interaction in
severe acute kidney	criteria of 2 or above	restriction in acute	the adjusted analysis
injury	[41] (yes/no)	kidney injury	described above; P-
			value 0.01

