The trial intervention is not blinded for investigators, clinical staff and patients, as blinding of IV fluid restriction versus standard care is not feasible. The statistician assessing all outcomes will be masked for the allocation. The data for 90-day and 1-year mortality will be collected from electronic patient records or central national registries in most participating countries. The remaining outcomes will be provided by local investigators, who are not blinded for the intervention, by entering data from patients' files. The management committee will write the preliminary abstract with the group allocation masked; this abstract will be published as a supplement to the primary trial report.^{5,6}

Outcome measures

Primary outcome measure

The primary outcome measure is all-cause mortality at day 90 after randomisation.

Secondary outcome measures

We have 7 secondary outcome measures:

 Number of participants with one or more serious adverse events (SAEs) in the ICU defined as ischaemic events (cerebral, cardiac, intestinal or limb ischaemia) or a new episode of severe AKI (modified KDIGO3⁷)

- Number of participants with one or more serious adverse reactions (SARs) to IV crystalloids in the ICU
- Days alive at day 90 without life support (vasopressor / inotropic support, invasive mechanical ventilation or renal replacement therapy (RRT))
- Days alive and out of hospital until day 90
- All-cause mortality at 1 year after randomisation
- Health-related quality of life (HRQoL) 1 year after randomisation measured using the EuroQoL EQ-5D-5L scores ⁸
- Cognitive function 1 year after randomisation as assessed by the telephone MINI-Montreal Cognitive Assessment (MINI-MoCA) score ⁹

Detailed definitions of the outcome measures are available in the protocol.

Missing data

If less than 5% of data required for any specific analysis on primary or secondary outcomes are missing, a complete case analysis will be performed. If more than 5% are missing, and it is concluded that data are not 'missing completely at random' (MCAR criterion),^{10,11} multiple imputation using chained equations will be performed by creating 25 input datasets under the assumption that the data are 'missing at random' (MAR criterion).^{12,13}

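### Above 5% missing, imputation and the best-worst/worst-best analysis both depend on first concluding that the data are not MCAR, so failing to reject MCAR counts as support for it at any missing fraction

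*Protocol*

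**What the plan says.** Protocol 10.2.4 sets a first threshold: "If less than 5% of data are missing for any primary or secondary outcome, a complete case analysis without imputation". Above 5%, "a statistician masked for the intervention will assess whether data are 'missing completely at random", on the basis of the pattern of missingness, and "Little's test will be used if doubt remains". Then: "If it is concluded that data are not MCAR, multiple imputation using chained equations will be performed".

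The SAP, under Missing data, carries the same double condition: "If more than 5% are missing, and it is concluded that data are not 'missing completely at random". It cites the reference for Little's test without naming the test in the text.

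Neither document sets an upper missing fraction, gives a significance level for Little's test, or states in words what is done above 5% when MCAR is accepted.

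The extreme-case analysis hangs on the same decision. Protocol 10.2.4: "If multiple imputation is used because of missing outcome data, we will use a best-worst worst-best case scenario as a sensitivity analysis". The SAP also makes it conditional on multiple imputation being used.

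Protocol 10.2 reads differently: "If there is more than 5% missing data for outcomes and/or covariates, we will impute the missing data using multiple imputations". That sentence has no MCAR condition, but it refers on to 10.2.4, which adds one.

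**The concern.** Not rejecting MCAR is weak evidence for it, particularly when the missing group is small. MCAR is also more than the analysis needs: imputation under MAR with an adequate model remains valid when MCAR holds. The gate therefore buys little, and it can switch off a correction that the SAP has already specified in detail (SMS-ICU, lactate, creatinine, infection site and other baseline variables).

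The second consequence is easier to miss. The best-worst/worst-best analysis is the plan's only stated check for data missing not at random. Accepting MCAR removes it, although MCAR is then the very assumption that most needs challenging.

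**Working it through.** **Plan's own figure.** The point disputes no number, but the sample size enters below. For 45% vs 38%, two-sided 5%, 80% power: n per arm = [1.960·√(2·0.415·0.585) + 0.842·√(0.45·0.55 + 0.38·0.62)]² / 0.07² = 776.6, so 777. The planned 1554 is reproduced.

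**Power of Little's test.** Inputs: n = 1554 (documents). Assumed: 12 fully observed covariates, missingness related to one of them at an odds ratio of 1.3 per SD, alpha 0.05. The statistic is approximately noncentral chi-square with 12 df and noncentrality λ = (ln 1.3)² × n_mis × n_obs / n, where (ln 1.3)² = 0.0688. The critical value is 21.03.

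| Missing | n_mis·n_obs/n | λ | Power |
|---|---|---|---|
| 6% | 87.6 | 6.0 | 0.30 |
| 10% | 139.9 | 9.6 | 0.49 |
| 15% | 198.1 | 13.6 | 0.67 |

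Power depends heavily on the inputs. For a 0.2 SD shift, with 10 down to 1 covariates, it is 19–47% at 6% missing and 54–88% at 20%. For a 0.3 SD shift at 20% missing it is 93–100%.

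**Bias in that same scenario.** Take 45% vs 38% mortality and an assumed covariate–death odds ratio of 1.5 to 3 per SD. With the same missingness model in both arms, the complete-case risk difference stays between −6.97 and −6.99 points at 6–15% missing, against −7.00. If only one arm has such missingness, the shift is about 0.15–0.35 points at 6% and 0.36–0.86 at 15%.

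**1-year scores.** Protocol Appendix 2 gives non-survivors the worst score on quality of life and cognition, so a known death is not missing. With 1-year mortality of 55% (Protocol 10.1.2) vs 0.85 × 55% = 46.75% and an assumed survivor mean of 0.70, the full difference is 0.70 × 0.0825 = 0.058. The complete-case arm mean is 0.70(1−d)r / [d + (1−d)r], where d is mortality and r is survivor response (assumed):

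- r = 0.85 control, 0.75 restrictive: 0.287 vs 0.322, difference 0.035
- reversed: 0.266 vs 0.344, difference 0.078
- r = 0.80 in both: 0.277 vs 0.334, difference 0.057

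About 10% of all participants are missing in each case. If death status is among the variables tested, its standardised shift is 1.1 to 1.2 SD, λ is roughly 170 to 200 on 13 df, and power is about 1.00. It is still about 1.00 at 5.9% missing (12% of survivors in each arm).

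**What lapses with the gate.** Let a fraction m be missing in each arm, with 45% vs 38% among those observed. Best-worst is 0.38(1−m) − [0.45(1−m) + m]; worst-best is [0.38(1−m) + m] − 0.45(1−m).

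| m | Best-worst | Worst-best |
|---|---|---|
| 6% | −12.6 points | −0.6 |
| 10% | −16.3 | +3.7 |
| 20% | −25.6 | +14.4 |

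Little's test need not warn of this. In a simulation (2000 replicates per setting) with deaths twice as likely to be missing in control and half as likely in the restrictive arm, it rejected in about 4–6% of runs at 6–30% missing, which is close to alpha. By direct calculation, complete cases would then turn −7.0 into −5.0 points at 6% missing and −3.5 at 10%.

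**The case against.** A reader might infer that a non-significant Little's test automatically sends any amount of missing data to complete-case analysis. The text does not say that. The masked statistician's judgement comes first, the test is used only if doubt remains, and complete-case analysis after accepting MCAR is implied, not written. Masking also limits the worry about a data-driven choice.

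It is also tempting to join the low power to the distortion of the 1-year difference (0.058 becoming 0.035 or 0.078). They belong to different scenarios. The survivors-only pattern should be visible at the judgement step, and the test would reject if death status were included. Where power is low, the computed bias is small. With equal response in both arms the 1-year difference hardly moves, although each arm mean is 10–12% too low.

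Nor is the gate useless in every case: imputation helps only if its model is adequate, and the 1-year scores need a survivors-only rule. MAR imputation does not in general correct the outcome-dependent scenario either; that example supports keeping the extreme-case analysis, not imputation as such. Finally, the SAP takes mortality from patient records or national registries in most countries, so exceeding 5% for the primary outcome is not shown to be likely.

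All of this stands. It lowers the stakes but does not justify the condition: no missing fraction overrides it, the accepted-MCAR branch is unspecified, and the sensitivity analysis disappears with imputation.

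**Conclusion.** The rule should be changed. Above 5% missing, both documents let a failure to reject MCAR stand as support for it at any missing fraction. Complete-case analysis is then the implied default and the best-worst/worst-best analysis is lost. Protocol 10.2 does not settle the matter, since its unconditional sentence refers to 10.2.4.

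The size is modest. Power of about 30% at 6% missing and 49% at 10% rests on the assumed 12 covariates, odds ratio of 1.3 and alpha of 0.05, none of which the documents give. The bias in the treatment difference there is probably well under one percentage point. No biased result is demonstrated, and a careful assessor should already reject MCAR for the 1-year scores. The clearest loss is the unreported sensitivity range, for example −16.3 to +3.7 points for 90-day mortality at an assumed 10% missing per arm.

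**What to change.** Let more than 5% missing alone trigger the SAP's multiple imputation (25 datasets, by arm), with 1-year scores imputed in survivors only, and the best-worst/worst-best analysis. Report the MCAR assessment descriptively and show the complete-case result alongside. Align Protocol 10.2, Protocol 10.2.4 and the SAP, including the number of imputed datasets (10 in the protocol, 25 in the SAP).

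The imputation is already planned, so the cost is wording and a little more analysis work. The SAP's summary of changes places final analyses in March 2022. For any outcome already analysed, the change should be reported openly as a later addition.

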11.1 Monitoring

The trial will be externally monitored according to the GCP directive and the monitoring and data verification plan including the documentation of informed consent of trial participants. The monitoring and data verification plan will be developed together with the GCP unit of Copenhagen University Hospital and adhered to by the staff monitoring trial sites in all countries. In addition, we will use central monitoring of site through the eCRF including adherence to the protocol.

11.2 Drug traceability measures

The volumes of IV fluid administered will be registered in the eCRF for every day the participant is in the ICU to a maximum of 90 days. The registration of the batch numbers and the expiry dates of the IV fluids and the identity of the clinician administering the fluid will be registered as per standard practice at the sites. These data will not be registered in the trial documents, but can be obtained by the Sponsor or the authorities if needed. We believe that this is a safe procedure because the IV fluids used in the CLASSIC trial has been in clinical use for many years and the safety of single doses cannot be questioned. The same procedure was approved by the Danish Medicines Agency in the CLASSIC pilot trial (EudraCT no. 2014-000902-37).

12 Legal and organisational aspects

12.1 Finance

12.1.1 Trial funding

The trial is funded by an unrestricted grant from the Novo Nordisk Foundation and Sofus Friis' foundation. None of the funding organisations have been or will be involved in the design, conduct, analyses, or reporting of the trial nor will they have ownership of the data.

12.1.2 Compensation

All trial sites will be paid DKK 3000 (400 EUR) for each participant with completed 1-year follow-up status to partly compensate for the increased workload regarding screening, consent, inclusion, dataentry and follow-up.

12.2 Insurance

In Denmark, the Patient Insurance Association insures all trial participants. Patient insurance will be ensured before initiating the trial in each participating country. We will use external funding for the costs of insurance.

12.3 Plan for publication, authorship and dissemination

All trial results whether positive, negative or neutral will be published preferably in a peer-reviewed medical journal. Furthermore, the results will be published at the CRIC home page (www.cric.nu). We will adhere to the CONSORT statement including the accountability of all patients screened (Appendix 10).

The CLASSIC trial protocol Page 35/82

Authorship will be granted according to the guidelines from the International Committee for Medical Journal Editors (ICMJE; http://www.icmje.org/recommendations/browse/roles-and-responsibilities/defining-the-role-of-authors-and-contributors.html).

The listing of authors will be as follows on the primary publication: [name] will be first author, [name] the second, [name] the third, the next authors will be the national investigators according to the number of included participants per country, then the other members of the Management Committee, the trial statistician and trial site investigators dependent on the number of included participants per site. [name] will be the last and corresponding author.

The Management Committee will grant authorship depending on personal input as per the Vancouver definitions. If a trial site investigator is to gain authorship on the primary publication, the site has to include 25 participants or more. If a site includes 50 participants, 2 authorships may be granted, at 75 participants 3 authorships and so on. Investigators on sites including less than 25 participants may be granted authorship on the long-term outcome publication if they contribute significantly as per the Vancouver definitions.

The DMSC and investigators not qualifying for authorship will be acknowledged with their names under 'the CLASSIC Trial investigators' in an *appendix* to the final manuscript.

The funding sources will be acknowledged, but they will have no influence on the data handling or analyses, the writing of the manuscript or the decision to publish.

12.4 Sub-studies

Sub-studies are planned at selected sites and more will be encouraged as long as they do not hamper the completion of the main protocol and can be conducted after approval of the specific protocol by the Management Committee and the authorities. Thus, specific protocols for any sub-studies will be submitted to and approved by the relevant authorities and ethic committees before the commencement of such studies. In Appendix 8, the presently proposed sub-studies are listed.

12.5 Intellectual property rights

The CLASSIC trial group owns the trial data. The Contract between the Sponsor and an investigator will be reviewed and approved by the Unit for Research and Innovation (Law and Contracts) of the Capital Region (https://www.regionh.dk/english/research-and-innovation/Pages/default.aspx) and by the Medical Director of Rigshospitalet, dr. [name].

12.6 Organisational framework

The CLASSIC trial will be managed by the Management Committee and overseen by the CRIC Steering Committee (Appendix 1). The day-to-day running of the trial will be done by the Sponsor, the Coordinating Investigator and the CRIC office.

The CLASSIC trial protocol Page 36/82

14.1 Appendix 1. Research programme organisation

The CLASSIC trial protocol Page 44/82

14.2 Appendix 2. Trial definitions

Definition of stratification variables

Site: all participating intensive care units (ICUs) will be assigned a number identifying the unit.

Metastatic cancer or hematologic malignancy:

- Metastatic cancer: proven metastasis by surgery, CT scan or any other method
- Haematological malignancy includes any of the following:
 - Leukaemia: Acute lymphoblastic leukaemia (ALL), acute myelogenous leukaemia
 (AML), chronic myelogenous leukaemia (CML), chronic lymphocytic leukaemia (CLL).
 - Lymphoma: Hodgkin's disease, and Non-Hodgkin lymphoma (e.g. small lymphocytic lymphoma (SLL), diffuse large B-cell lymphoma, follicular lymphoma and mantle cell lymphoma)
 - Hairy cell leukaemia (HCL), marginal zone lymphoma, Burkitt's lymphoma, posttransplant lymphoproliferative disorder (PTLD), T-cell prolymphocytic leukaemia (T-PLL), B-cell prolymphocytic leukaemia (B-PLL), Waldenström's macroglobulinemia and other NK- or T-cell lymphomas
 - Multiple myeloma/plasma cell myeloma

Definition of the inclusion criteria

Age: the age of the participant in whole years at the time of randomisation. The age will be calculated from date of birth.

Admitted to the ICU or plan to be admitted to the ICU: We will only recruit sites that have the status as an ICU. These may oversee beds defined as high-dependency, step-up or step-down beds. We will consider these as being part of the trial site ICU if staff trained in the protocol looks after the patients in these beds. The medical doctors at the site ICUs may enrol patients from other locations in the hospital (e.g. emergency departments, general wards or the recovery room) if the patient for clinical reasons is planned to be admitted to the ICU.

Septic shock: We will define septic shock at the time of screening according to the Sepsis-3 criteria [9] i.e.:

- Suspected or confirmed site of infection or positive blood culture AND
- Ongoing infusion of vasopressor/inotrope agent (norepinephrine, epinephrine, phenylephrine, vasopressin analogues, angiotensin, dopamine, dobutamin, milrinone or levosemindan) to maintain a mean arterial blood pressure of 65 mmHg or above AND
- Lactate of 2 mmol/L or above in any plasma sample performed within the last 3-hours prior to screening

Have received at least 1 L of IV fluid in the last 24-hours prior to screening: We will count all crystalloids (isotonic saline, Ringer's and Plasmalyte™ solutions) colloids (albumin 4, 5 or 20%, gelatine, hydroxyethyl starch and dextran solutions) and blood products (units or red cells, plasma or

The CLASSIC trial protocol Page 45/82

platelets) the participant has received according to the source data within the last 24-hours independent of location (in- or pre-hospital) including fluids with IV medication and IV nutrition. Intraosseous fluid will be counted as IV.

Definition of the exclusion criteria

- -Septic shock for more than 12 hours at the time of screening: Septic shock according to the Sepsis-3 criteria [9] (definition given above) for more than 12 hours at the time of screening. We will use infection and infusion of vasopressor/inotrope agent for more than 12 hours as a cutoff, as the plasma lactate value may change during the course of treatment
- -Life-threatening bleeding: clinical bleeding needing transfusion of blood products as defined by the clinicians
- -Acute burn injury of more than 10% of the body surface area: burn injury leading to the present ICU admission. Patients with burn injury who are readmitted to the ICU or were initially care for in a general ward and admitted to the ICU for infection may be screened to enrolment. The latest documented estimate of the burn area will be used as these may be down-graded after the initial assessments.
- -Known pregnancy: women with known pregnancy based on clinical examination, the history or human chorionic gonadotropin (hCG). We will not demand negative hCG-status in all eligible fertile women, because (i) screening for enrolment has to be done within the time window (waiting for the hCG result will delay screening and result in fewer fertile women included), (ii) the pregnancy rate is very low in ICU patients with septic shock and (iii) trial participation will not endanger the woman or the foetus. The same procedure was approved by the Danish Medicines Agency in the TARTARE 2S trial (EudraCT no. 2015-005112-15), which has many similarities to the CLASSIC trial (ICU patients with septic shock randomized to protocolised titration of an approved medicine (noradrenalin).
- -Consent not obtainable according to national regulations: patients where the clinician or investigator is unable to obtain the necessary consent before inclusion of the patient according to the national regulations.

Definition of baseline variables

- -Sex: the genotypic sex of the participant
- -Age: defined in inclusion criteria
- -Date of admission to hospital: the date of admission to the first hospital the participant was admitted to during the current hospital admission
- -Date and time of admission to the ICU (or high-dependency or step-up/step-down beds; see inclusion criteria): the date of admission to the first ICU the participant was admitted to during the current hospital admission
- -From where was the participant admitted to ICU
 - Emergency department or directly from the pre-hospital setting:
 Accident/Emergency/Casualty/Acute department in the same or another hospital or direct admission to the ICU by an ambulance service or similar

The CLASSIC trial protocol Page 46/82

- Hospital ward: Any location in the same or another hospital not covered in the other 3 categories
- Operating or recovery room: including surgical theatre, endoscopy and angiography suite and any recovery facilities observing patients following invasive procedures.
- Another ICU: either within the same or another hospital

Focus of infection (documented or suspected):

- o Pulmonary: e.g. pneumonia, or empyema
- Gastrointestinal infection: e.g. primary, secondary or tertiary peritonitis, abscess, cholangitis, cholecystitis, or invasive diarrhoeal disease
- Urinary tract infection: e.g. urinary tract infection, or pyelonephritis
- o Skin or soft tissue infection: e.g. cellulitis, phlegmon, erysipelas, or fasciitis
- Other: other infectious focus documented or suspected including meningitis, endocarditis, osteomyelitis, arthritis and bacteraemia
- -Co-morbidities, must have been present in the past medical history prior to ICU admission and are defined as follows:
 - o Active hematologic cancer: defined in the stratification variables
 - o History of metastatic carcinoma: defined in the stratification variables
 - History of ischemic heart disease or heart failure: previous myocardial infarction, invasive intervention for coronary artery disease, stable or unstable angina, NYHA class 3 or 4 or measured LVEF < 40%.

 - Chronic dialysis: use of renal replacement therapy at least once a week e.g. chronic haemodialysis or haemofiltration, peritoneal dialysis
- Blood values, interventions and vital parameters:
 - o Participant weight: measured or estimated in kg
 - Highest plasma lactate value within the last 3 hours of randomisation: in mmol/L
 - O Highest dose of noradrenaline within the last 3 hours of randomisation: highest infusion rate in μg/kg/minVolumes of IV fluid within the last 24 hours of randomisation: all crystalloids (any saline, NaHCO3-, Ringer's and Plasmalyte™ solutions), colloids (albumin 4, 5 or 20%, gelatine, hydroxyethyl starch and dextran solutions) and blood products (units of red cells, plasma or platelets) the participant has received within the last 24-hours independent of location (in- or pre-hospital) including fluids with IV medication and IV nutrition. Intraosseous fluid will be counted as IV

0

 Use of systemic (IV, IM or oral/per GI tube) corticosteroids in the last 24 hours of randomisation including any dose of hydrocortisone, methylprednisolone, dexamethasone or prednisolone

The CLASSIC trial protocol

- Highest plasma creatinine value within the last 24 hours of randomisation: in μmol/L
- Use of acute renal replacement therapy in the last 3 days prior to randomisation: any form
 of renal replacement therapy (e.g. dialysis, hemofiltration or hemo-diafiltration) at any rate
 in the last 72 hours, which has been initiated during the current hospitalisation (including
 any stay in another hospital immediately prior that in the site)
- \circ Habitual plasma creatinine value prior to current hospitalisation: estimated or measured in μ mol/L. If no there are no values recorded in source data, we will estimate habitual plasma creatinine

-The simplified mortality score (Appendix 6) is based on 7 variables obtained in the 24 h prior to randomisation of a patient into the trial [43]. The variables include:

- o Age: defined in inclusion criteria
- Lowest systolic blood pressure: either invasive or non-invasive in mmHg. In case of cardiac arrest within the 24-h period '0' will be registered.
- Acute surgical admission: Surgery during current hospital admission that was added to the operating room schedule.
- o Hematologic malignancy or metastatic cancer: Defined in the stratification variables.
- Vasopressors/inotropes: Use of continuous infusion of vasopressor or inotrope (defined in the inclusion criteria).
- Respiratory support: Use of invasive or non-invasive mechanical ventilation including continuous mask CPAP or CPAP via tracheostomy within the last 24 hours prior to randomisation. Intermittent CPAP and high flow nasal cannula oxygen therapy are NOT considered as respiratory support
- Renal replacement therapy: Use of acute or chronic intermittent or continuous renal replacement therapy.

Definition of daily collected variables:

- -Fluid input and output in mL cumulated from the 24-h ICU charts
 - Total volume and specific type of IV isotonic crystalloids: isotonic saline and buffered solutions: Ringer's lactate, Ringer's acetate and PlasmaLyte™
 - o Total volume of other IV fluids: e.g. <10% glucose, glucose-potassium, sodium-potassium-chloride, half-saline
 - Total volume of albumin (4, 5 or 20% solutions combined)
 - o Total volume of fluids with medications: both parenteral and enteral
 - Total volume of fluids with enteral and parenteral nutrition: e.g. enteral nutrition solutions and >10% glucose, protein or lipid solutions given parenterally or enterally
 - o Total volume of non-nutritional enteral/oral fluids: e.g. water or soft drinks
 - o Total volume of blood products: defined in inclusion criteria
 - Urinary output on this day
 - o Any fluid volume removed during renal replacement therapy
 - Total volume of other losses on this day including drainage, aspirates, stools and bleeding

-Major protocol violation on this day:

The CLASSIC trial protocol Page 48/82

- \circ Restrictive group: IV fluids given without one of the extenuating circumstances occurring on this day (y/n)
- Standard care group: the violations (no IV fluid given) will be assessed from all the day form registrations regarding fluid input at the end of trial for each participant
- -Use of infusion of vasopressor or inotrope on this day: defined in the inclusion criteria
- Use of systemic corticosteroids on this day: defined in the baseline data
- -Use of mechanical ventilation on this day: invasive mechanical ventilation as the use of positive pressure ventilation using a ventilator via a cuffed tube (oral, nasal or tracheostomy). CPAP is NOT mechanical ventilation.
- -Use of renal replacement therapy on this day: any form of renal replacement therapy (e.g. dialysis, hemofiltration or hemo-diafiltration) at any rate on this day.
- -Plasma concentration of creatinine in µmol/L on this day

Definition of outcome measures

Primary outcome:

90 day mortality: death from any cause within 90 days post-randomisation.

Secondary outcomes:

- -Serious adverse events as at least one episode of either the following observed in the ICU:
 - Ischemic events defined as either
 - o Cerebral ischemia defined as any form of cerebral ischemia on a CT- OR MRI scan
 - Acute myocardial ischemia defined as participant with acute myocardial infarction (STelevation myocardial infarction or non-ST elevation myocardial infarction) or unstable
 angina pectoris according to the criteria in the clinical setting in question (e.g. elevated
 biomarkers, ischemic signs on ECG and clinical presentation) AND the participant
 received treatment as a consequence of this (reperfusion strategies (PCI/thrombolysis)
 OR initiation/increased antithrombotic treatment).
 - Intestinal ischemia defined as ischemia verified by endoscopy OR open surgery OR CTangiography.
 - Limb ischemia defined as clinical signs AND need of open/percutaneous vascular intervention, amputation OR initiation/increased antithrombotic treatment.
 - A new episode of severe acute kidney injury defined as modified KDIGO3 [41]: a 3.0 times increase in baseline p-creatinine, or increase in p-creatinine to ≥354 μmol/L, or use of renal replacement therapy (any form) in participants who did not receive this before randomisation.
- -Serious adverse reactions: total number of SARs and number of SARs per participant in the ICU. Serious adverse reactions are defined below.

The CLASSIC trial protocol Page 49/82

- -Number of days alive without life support at day 90: will be assessed from the use of life support including vasopressor/inotrope, mechanical ventilation and renal replacement therapy as defined in the inclusion criteria, baseline and daily variables. Total number of days alive without all of the 3 life supporting interventions within 90 days after randomisation.
- -Days alive and out of hospital at day 90: will be assessed from the discharge date from the index hospitalisation, the number of days readmitted to hospital (if any) and date of death, if relevant, within the 90-day period
- -1-year mortality: landmark mortality 1-year post-randomisation. If the participant has deceased, date of death will be registered.
- -HRQoL at 1-year (+/- 2 weeks): EQ-5D-5L and EQ-VAS scores (https://euroqol.org/) obtained by survey by mail or phone as chosen by the participant. Non-survivors will be given the worst possible score. If the participant is incapable of answering the questionnaire (e.g. due to cognitive impairment or coma) we will ask proxies to assess HRQoL for the trial participant (proxy point of view) using the questionnaire aimed for proxies. Non-survivors will be given the worst possible score. EQ-5D-5L will be converted to an index value in combination with the EQ-VAS quantitative measure (0-100 points) quantifying self-rated health
- -Cognitive function at 1-year (+/- 2 weeks): the Montreal Cognitive assessment (MoCa) MINI score (or '5-miniute protocol') using the translations of the MoCa full v. 7.1 (http://www.mocatest.org/). The score will be obtained in all survivors by interview as this was recommended to be the test of cognition in a core outcome set for patients with acute respiratory failure following a modified Delphi process involving patients, researchers and clinicians from multiple continents (http://www.improvelto.com/). Non-survivors will be given the worst possible score. The cognitive function score will be conducted before HRQoL to ensure an equal procedure and avoid that patients are disturbed or tired from the HRQoL score.

If the MoCa MINI, which is validated for phone interview [52], has not been released at the time of the first assessment (1-year after randomisation of the first patient), we will adapt the MoCa MINI from the MoCa full v. 7.1.

SARs will be defined as follows:

- -General tonic-clonic seizures: stiffening and/or jerking movements of all 4 extremities in a patient who becomes or is unconscious in the ICU after randomisation
- -Anaphylactic reactions defined as urticarial skin reaction **AND** at least one of the following observed in the ICU after randomisation
 - Worsened circulation (>20% decrease in blood pressure or >20% increase in vasopressor dose)
 - Increased airway resistance (>20% increase in the peak pressure on the ventilation)
 - Clinical stridor or bronchospasm
 - o Subsequent treatment with bronchodilators

The CLASSIC trial protocol Page 50/82

- -Central pontine myelinolysis seen on CT or MRI scan within the 90-day period after randomisation
- -Hypernatremia defined as p-Na > 159 mmol/L on any plasma sample, including point-of-care testing, done in the ICU after randomisation
- -Severe hyperchloraemic acidosis defined as pH < 7.15 AND p-chloride > 115 mmol/L on any plasma sample, including point-of-care testing, done in the ICU after randomisation
- -Severe metabolic alkalosis defined as pH > 7.59 AND SBE > 9 mmol/L on any plasma sample, including point-of-care testing, done in the ICU after randomisation

